7.6 Efficacy Analyses

Efficacy endpoints are defined in **Appendix B**. Only efficacy endpoint events adjudicated by the CEC will be used in the secondary efficacy analyses.

7.6.1 Secondary Efficacy Endpoints

While the primary objective of this study is to determine the safety of PZ-128, secondary analyses will be used to evaluate potential efficacy signals that will allow an assessment of the comparative risk/benefit calculus of the treatment in determination of a future Phase 3 study.

Specific secondary efficacy outcome measures include:

- incidence of the composite endpoint of major adverse cardiac events (MACE)- any of cardiovascular death, non-fatal myocardial infarction, non-fatal stroke, recurrent ischemia requiring hospitalization or urgent coronary revascularization with either CABG or subsequent PCI evaluated through 30 days and 90 days after treatment;

- incidence of the individual components of the MACE composite as measures of potential clinical benefit evaluated through 30 days and 90 days after treatment:
 - cardiovascular death
 - non-fatal MI
 - non-fatal stroke
 - recurrent ischemia requiring hospitalization
 - urgent coronary revascularization
- incidence of definite or probable stent thrombosis evaluated through 30 days and 90 days after treatment;
- effect of the investigator choice of P2Y₁₂ inhibitor (i.e., clopidogrel versus prasugrel/ticagrelor) on the individual components of the MACE composite measure through 30 days and 90 days post treatment.

7.6.2 Methodology

The proposed phase 2 study is not of sufficient size or of sufficient follow-up duration to allow analysis of clinical event rates.

Two alternative approaches will be used to evaluate the differences in risk of the various secondary outcome measures. The first will utilize generalized linear models analogous to those used for the safety outcomes. In addition because each of these outcome measures can be evaluated using a time to event approach, survival analyses will be used to examine those outcomes. Kaplan-Meier estimates of the cumulative risk of each outcome will be calculated to investigate differences between the treatment groups in the time to occurrence, and a Cox Proportional hazard model that accounts for the risk stratification variables described above will be used to assess risk differences in the 3 treatment groups. All of these analyses will be interpreted descriptively, with no adjustment for multiple comparisons. We anticipate that some analyses will be conducted for specific subgroups (e.g., influence of baseline risk factors, concomitant therapies), but these subgroup analyses will again be considered exploratory and treated as descriptive analyses. Details will be provided in the SAP. Generalized linear models comparable to those used for the safety outcomes will also be used to evaluate the effect of investigator choice of P2Y₁₂ inhibitor on each of the MACE components.

7.7 Determination of Sample Size/Power

Power calculations were used to evaluate the size of non-inferiority margins that were able to be detected from a study of 600 participants, 400 of whom are randomized to PZ-128 and 200 of whom are randomized to placebo. Available data on bleeding rates from previous studies [29, 32, 33] suggest that the incidence of bleeding in the placebo arm is likely to be in the range of 2% to 6%. Furthermore, the sponsor assumes that the true difference in the incidence

of the participants on the PZ-128 arms and those in the placebo arms are likely to be in the range of 0% to 2%. Based on these assumptions, the table below shows the minimum non-inferiority margin that could be demonstrated with at least 80% power, where that non-inferiority margin is based on the upper limit of the 95% confidence interval identified above. This sample size is adequate to demonstrate acceptable upper safety bounds.

True Incidence or Risk of Bleeding for placebo	Minimum Demonstrable Non-inferiority margin	
	True Incidence Difference of 0%	True Incidence Difference of 2%
2%	2.6%	5.0%
3%	3.2%	5.5%
4%	3.7%	5.9 %
5%	4.1%	6.3%
6%	4.4%	6.6%

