Clinical evaluations including physical examinations, vital signs, laboratory tests, electrocardiograms and the assessment of adverse events will be performed for all subjects during hospitalization and at follow-up time points as measures of the safety profile.

Randomization: Randomization will be conducted prior to the diagnostic angiography.

Stratification: Randomized assignment of PZ-128 and placebo will be stratified for whether the cardiac catheterization ± PCI is being done on an elective or urgent basis at the time the operator decides to perform the procedure.

Sample Size/Power: The current design anticipates a sample size of 600 subjects who will undergo non-emergent cardiac catheterization ± PCI. The sponsor anticipates that the incidence of major plus minor bleeding among placebo-treated subjects will range from 2% to 6% on the basis of historical experience. Given the anticipated sample sizes and estimated range of incidences associated with placebo, the study will be able to demonstrate that the bleeding risk of PZ-128 is non-inferior to the risk associated with placebo with non-inferiority margins in the range of 2.6 to 7.6%, depending on the underlying bleeding risk of placebo. Given the anticipated benefits of PZ-128, these non-inferiority margins are reasonable for the planned safety decisions generated from this trial.

Statistical Methods: All subjects who are randomized will be considered evaluable for the analyses. The following statistical analysis will be provided for the primary endpoint. The point estimate of the difference in risk of any event of non-CABG TIMI major plus minor bleeding through 30 days post treatment for between PZ-128 and placebo (e.g., Pr (Event in PZ-128 patient)-Pr (Event in placebo patient)), and corresponding lower one-sided 95% confidence interval will be presented. These estimates will be generated using subjects who underwent diagnostic angiography for all PZ-128 treatment arms pooled across both doses (~400 subjects) and all placebo (~200 subjects) and descriptive results will also be generated for each individual dose. The proposed phase 2 study is not of sufficient size or of sufficient follow-up duration to allow formal analysis of clinical efficacy.

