6.3 Study Population

This study will be conducted at approximately 3 clinical sites in the United States (US) without any pre-specified minimum/maximum enrollment target per site or per the study stratum:

- Inova Heart and Vascular Institute, Inova Fairfax Hospital (Falls Church, VA)
- Tufts Medical Center (Boston, MA)
- UMass Memorial Medical Center (Worcester, MA)

This study will enroll a total of approximately 600 subjects. Subjects who are randomized, but who discontinue from the study prior to receiving any amount of study drug may be replaced.

The sponsor estimates a maximum screen failure rate of 20% (i.e., those who sign consent but fail to be randomized for any reason). Therefore, the study will require a maximum of 720 prospective participants to sign consent in order to successfully randomize 600 subjects.

Subjects must meet all inclusion criteria and none of the exclusion criteria to be enrolled/randomized and receive study drug assignment.

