7.5.4 Methodology

The primary objective of this study is to evaluate the safety of two dose levels of PZ-128 compared to placebo as measured by the incidence of TIMI major plus minor bleeding not related to CABG through 30 days after treatment. Specifically, the study will be designed to test the hypothesis that from a safety perspective, PZ-128 is non-inferior to placebo, where non-inferiority is demonstrating that the difference in risk of bleeding incidence between the two treatments is less than a specified clinically important margin; the acceptable safety margin will depend in part on the efficacy benefit found for PZ-128. Specifically, the analysis of the bleeding outcome variables will assess the risks of bleeding on the two treatment regimens by generating point and one-sided 95% confidence interval estimates of the risk difference using the following formula:

$$\text{Risk Difference} = \pi_{\text{PZ-128}} - \pi_{\text{Pbo}}$$

where $\pi_{\text{PZ-128}}$ is the bleeding incidence across the two PZ-128 arms and π_{Pbo} is the bleeding incidence for the placebo arm. The point and interval estimates for this risk difference will be obtained using a generalized linear model with the binomial distribution assumption and an identity link. To address the potential underlying risk differences associated subpopulations defined by underlying subject risk and whether or not the subject received CABG, those factors will be included in the model. The robust variance estimator as defined by Liang and Zeger [49] will be used to generate the interval estimates. Comparable models will be used to generate estimates for both the primary outcome and the secondary outcomes defined above.

Adverse Events

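### The Section 7.7 margins carry about 70% power, not 80%, at the stated one-sided 95% bound, and the synopsis maximum of 7.6% disagrees with the table maximum of 6.6%

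*Combined protocol and SAP*

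**What the plan says.** Section 7.5.4 sets the primary analysis as "generating point and one-sided 95% confidence interval estimates of the risk difference", PZ-128 (both doses pooled) minus placebo. It fixes no margin, because "the acceptable safety margin will depend in part on the efficacy benefit found for PZ-128". The synopsis gives the same level: "corresponding lower one-sided 95% confidence interval will be presented".

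Section 7.7 takes 600 subjects, "400 of whom are randomized to PZ-128 and 200 of whom are randomized to placebo", a placebo bleeding incidence of 2% to 6%, and a true difference of 0% to 2%. It then says that "the table below shows the minimum non-inferiority margin that could be demonstrated with at least 80% power", and that this "margin is based on the upper limit of the 95% confidence interval identified above". The printed margins for placebo incidences of 2, 3, 4, 5 and 6% are:

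- true difference 0%: 2.6, 3.2, 3.7, 4.1, 4.4%
- true difference 2%: 5.0, 5.5, 5.9, 6.3, 6.6%

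For the same sample size and placebo range, the sample-size paragraph of the synopsis promises non-inferiority "with non-inferiority margins in the range of 2.6 to 7.6%, depending on the underlying bleeding risk of placebo".

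A smaller figure is in Section 6.3. It assumes that at most 20% of those who sign consent fail to be randomized, and concludes that "the study will require a maximum of 720 prospective participants to sign consent in order to successfully randomize 600 subjects".

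**The concern.** The confidence level, power, group sizes and incidences are all stated, so the margins can be recomputed without any outside figure. They come out too small for the level named. The synopsis and the table also differ by a full percentage point at the upper end, which needs no calculation to see.

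This matters because the trial is described as a non-inferiority study of bleeding safety, and the table is the only numerical support for 600 subjects and for the claim that this number is adequate. A monitoring board, ethics committee or funder reading it is told that the trial can exclude a smaller excess of bleeding, at the quoted power, than it can. The chance of missing a printed margin when the planning assumptions are true is about 30%, not at most 20%.

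**Working it through.** **Inputs.** n1 = 400 and n0 = 200; p0 = 2% to 6%; true difference d = 0% or 2%, so p1 = p0 + d; power 80% (all Section 7.7). One-sided 95% bound (Section 7.5.4 and synopsis), so z = 1.645. For 80% power, z = 0.8416.

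**Formulas.**

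- SE = sqrt(p1(1 − p1)/400 + p0(1 − p0)/200)
- Margin for 80% power = d + (z + 0.8416) × SE
- Power at a printed margin M = Φ((M − d)/SE − z)

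**Reproducing the printed table.** At one-sided 95% the multiplier is 1.645 + 0.8416 = 2.486, and no cell reproduces. At one-sided 90% it is 1.2816 + 0.8416 = 2.123, and every cell reproduces once rounded up to the next 0.1. For placebo 2% and d = 0, SE = 1.212%, and 2.123 × 1.212% = 2.574%, printed as 2.6%. For placebo 6% and d = 2%, SE = 2.159%, and 2% + 2.123 × 2.159% = 6.583%, printed as 6.6%. Ordinary rounding does not reproduce all ten.

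| Placebo, d | Printed margin | One-sided 90% margin | One-sided 95% margin | Power at printed margin, normal | Power, exact Wald |
|---|---|---|---|---|---|
| 2%, 0% | 2.6 | 2.574 | 3.015 | 69.1% | 71.7% |
| 3%, 0% | 3.2 | 3.137 | 3.673 | 69.9% | 72.8% |
| 4%, 0% | 3.7 | 3.603 | 4.220 | 70.4% | 72.6% |
| 5%, 0% | 4.1 | 4.007 | 4.693 | 70.1% | 72.3% |
| 6%, 0% | 4.4 | 4.367 | 5.114 | 69.0% | 70.6% |
| 2%, 2% | 5.0 | 4.957 | 5.463 | 69.5% | 71.9% |
| 3%, 2% | 5.5 | 5.451 | 6.042 | 69.4% | 71.1% |
| 4%, 2% | 5.9 | 5.874 | 6.537 | 68.9% | 70.7% |
| 5%, 2% | 6.3 | 6.248 | 6.975 | 69.3% | 70.8% |
| 6%, 2% | 6.6 | 6.583 | 7.368 | 68.7% | 69.7% |

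The exact column sums the binomial probabilities of all outcomes whose unadjusted one-sided 95% Wald upper bound lies below the printed margin.

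**Sensitivity to method, still at one-sided 95%.** Exact power at the printed margins is 70.4-74.8% with the Farrington-Manning score bound, 71.4-75.4% with Newcombe's interval and 59.4-63.9% with a continuity-corrected Wald bound. A pooled variance in the normal approximation gives 61.2-65.3% in the 2% column; the 0% column does not change, because p1 = p0. No method tried reaches 80%.

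**Margins that do give 80% power.** Unpooled and rounded up: 3.1, 3.7, 4.3, 4.7, 5.2% (d = 0) and 5.5, 6.1, 6.6, 7.0, 7.4% (d = 2%). By exact Wald enumeration on a 0.05-point grid: 2.90, 3.50, 4.10, 4.60, 5.00% and 5.35, 5.95, 6.45, 6.90, 7.20%. The printed cells are therefore low by 0.5 to 0.8 points (unpooled, rounded up) or 0.3 to 0.6 points (exact).

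**Sample size for the printed margins.** The placebo group would need (p0(1 − p0) + p1(1 − p1)/2) × 2.486² / (M − d)² subjects. This is 261 to 273 across the ten cells, or 783 to 819 in total at 2:1.

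**Synopsis range.** The lowest and highest margins under each assumption, with the unpooled then the pooled value for the highest:

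- one-sided 95%: 3.015; 7.368 or 7.613
- one-sided 90%: 2.574; 6.583 or 6.793
- one-sided 97.5%: 3.397; 8.048 or 8.325

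None of these gives 2.6 and 7.6 together.

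**Consent count.** With 20% of consenting subjects lost, 600/0.80 = 750 consents are needed; 720 × 0.80 = 576 would be randomized.

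**The case against.** The strongest reply is that nothing downstream depends on the table. Section 7.5.4 fixes no margin, and the primary estimate and its interval are the same whatever Section 7.7 says. The synopsis already calls margins up to 7.6% reasonable, and the corrected maximum is 7.4% (unpooled, rounded up) or 7.2% (exact). On the protocol's own terms the conclusion that 600 is adequate survives; only the pooled value, 7.613%, passes 7.6%, and by a hair. That limits the consequence and is why no change in sample size is asked for. It does not make the power statement true.

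A second reply is that the corrected margins depend on the method, and that the planned analysis, a covariate-adjusted identity-link binomial model with robust variance, was not modelled here. This is fair, and no single set of figures should be presented as the only correct one. But nothing in the plan suggests that adjustment would recover about 10 points of power.

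Third, the 7.6% may be a typing slip for 6.6%, since the lower end equals the table minimum. That is plausible but cannot be shown from the documents. Changing it to 6.6% would only bring the synopsis into line with a table that is itself wrong at the stated level.

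Finally, the consent count has nothing to do with power. It is a separate minor correction.

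**Conclusion.** The point holds. With 400 against 200 subjects and a one-sided 95% upper bound, the Section 7.7 margins have about 69-70% power by the unpooled normal approximation and 70-73% by exact Wald enumeration, in every cell, against a claim of at least 80%. The low end of the demonstrable range is about 2.9 to 3.1%, not 2.6%. The synopsis and the table disagree on the maximum, 7.6% against 6.6%.

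The result rests on reading the bound in Section 7.7 as the one-sided 95% limit of Section 7.5.4. The synopsis calls its bound lower, but Section 7.7 names the upper limit, which is the one that can exclude excess bleeding. It also assumes 600 analysable subjects, with no allowance for losses. That a 90% bound was used is an inference from the ten matching cells; the shortfall does not depend on it. What needs correcting is the planning statement, not the trial's size or analysis.

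**What to change.** 1. In Section 7.7, replace the table with margins computed at the stated one-sided 95% bound and name the method. Under the unpooled normal approximation, rounded up, these are 3.1, 3.7, 4.3, 4.7, 5.2% (true difference 0%) and 5.5, 6.1, 6.6, 7.0, 7.4% (true difference 2%). Alternatively, keep the printed margins and say that they give about 70% power, or that they assume a one-sided 90% bound if that was the calculation.
2. Make the synopsis range agree with whichever table is kept: 3.1 to 7.4% for the unpooled replacement, or 2.6 to 6.6% if the printed margins stay.
3. As a separate minor correction, give 750 consents in Section 6.3.

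The cost is a few figures and sentences. The stated margins or the stated power become somewhat less favourable. Sample size, design and analysis stay as they are.

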7.8 Interim Analysis

Although no formal stopping boundaries will be utilized, one interim safety analysis will be performed at approximately 1 year following the enrollment of the first subject, or after enrollment of 50% of the study population, whichever occurs first. The Data and Safety Monitoring Board (DSMB) will be provided point and interval estimates of PZ-128 benefit at the time of that analysis based on survival estimates, and will evaluate evidence of bleeding risk in light of the potential efficacy benefits in making recommendations about stopping the trial.

An independent DSMB, as described in **Section 9.3.1**, will monitor safety data on an ongoing basis to ensure that subject safety is not compromised. The DSMB-supporting statistician will have access to the randomization code to allow grouping of the safety data. The DSMB will receive blinded data but has the option to unblind the data if deemed warranted. The DSMB will make safety recommendations for the alteration or termination of the study to the study sponsor.

7.9 Other Analyses

7.9.1 Pharmacokinetics

The plasma portion of the blood samples from each consenting participant will be assayed at a centralized lab for PZ-128 under non-GLP conditions at baseline and select time points following the start of the study drug administration as specified in **Section 6.6.3**. PK parameters will be calculated over time (C_{max} , AUC, $t_{1/2}$, Clearance and Distribution) and will be summarized by dose level. Data will be presented using graphical summaries and descriptive statistics.

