3.0 LIST OF ABBREVIATIONS AND DEFINITIONS OF TERMS

ACC	American College of Cardiology
ACS	Acute coronary syndrome(s)
ACT	Activated clotting time
ADP	Adenosine diphosphate
AE	Adverse event
AHA	American Heart Association
ALT	Alanine aminotransferase
AMI	Acute myocardial infarction
API	AmbioPharm, Inc.
aPTT	Activated partial thromboplastin time
ARC	Academic Research Consortium
ASA	Acetyl salicylic acid (aspirin)
AST	Aspartate aminotransferase
AUC	Area under plasma concentration-time curve from zero to infinity
AYPGKF	Ala-Tyr-Pro-Gly-Lys-Phe (PAR4 agonist peptide)
BP	Blood pressure
BUN	Blood urea nitrogen
CABG	Coronary artery bypass graft surgery
CAD	Coronary artery disease
cAMP	Cyclic adenosine monophosphate
CBC	Complete blood count
CEC	Clinical Events Committee
CFR	USA Code of Federal Regulations
CHF	Congestive heart failure
CI	Confidence interval
CK	Creatine kinase
CKD	Chronic kidney disease
CK-MB	Creatine kinase-myocardial band
C _{max}	Maximum plasma (peak) drug concentration
CRF	Case report form
CRS	Central Randomization Service

CSR	Clinical study report
cTn	Cardiac troponin
CVA	Cerebrovascular accident
CXR	Chest x-ray
DAPT	Dual anti-platelet therapy
DSMB	Data and Safety Monitoring Board
ECG, EKG	Electrocardiogram
eCRF	Electronic case report form
EDC	Electronic data capture
Endpoint	A status of the subject that constitutes the ‘endpoint’ of a subject’s participation in a clinical study and that is used as the final outcome
FACS	Fluorescence activated cell sorter
FAX	Telefacsimile
FDA	Food & Drug Administration, USA
GCP	Good Clinical Practice
GLP	Good Laboratory Practices
GMP	Good Manufacturing Practices
GPI	Glycoprotein IIb/IIIa inhibitors
GPCR	G protein coupled receptor
GPRP	Gly-Pro-Arg-Pro (fibrinogen inhibitor)
h	Hour(s)
Hct	Hematocrit
HDL-C	High-density-lipoprotein cholesterol
Hgb	Hemoglobin
HPR	High platelet reactivity
HR	Heart rate
IATA	International Air Transport Association
ICH	International Conference on Harmonisation of Technical Requirements for Registration of Pharmaceuticals for Human Use
IFU	Instructions for Use
IND	Investigational New Drug Application
INDSR	Investigational New Drug Safety Report
INR	International Normalized Ratio

IPA	Inhibition of platelet aggregation
IP	Investigational Product(s)
IRB	Institutional Review Board
IPA	Inhibition of platelet aggregation
ITT	Intent-to-treat- refers to a study population for statistical analysis
IUD	Intrauterine device
IV	Intravenous, intravenously
IVRS	Interactive voice response system

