platelet agent during PCI as discussed above. The subgroup of subjects on concomitant ASA therapy revealed stronger apparent effects of PZ-128 on inhibition of maximal and final aggregation to 8 μM ($P=0.084$) and 12 μM ($P=0.06$) SFLLRN in the 0.5 mg/kg dose cohort. The subgroup of subjects receiving ASA in the 0.5 mg/kg dose cohort had 60-80% average inhibition of final aggregation to 8 μM SFLLRN at 30 min-2 h and 100% inhibition by 6 h. There was 40% of recovery to aggregation to 8 μM PAR1 agonist by 24 h and 60% recovery by 192 h (the next sampling time point). Higher concentrations of PAR1 agonist (e.g., 20 μM SFLLRN) showed 80% recovery of aggregation by 24 h and 95% by 192 h in the 0.5 mg/kg dose cohort receiving concomitant ASA. At high doses of 1-2 mg/kg, PZ-128 gave significant mean ~90-100% inhibition at 1-2 h time points regardless of whether the subjects received ASA or not.

[figure not shown]
At 0.3-0.5 mg/kg doses where anti-PAR1 effects on platelet aggregation were observed at 30 min-2 h, drug levels of PZ-128 achieved therapeutic concentrations of 1-3 μM (~920-2800 $\mu\text{g/mL}$). Peak drug levels (C_{max}) occurred at the end of the 1 h or 2 h infusion in all dose cohorts with a terminal $t_{1/2}$ of elimination of 1.3-1.8 h. Drug was undetectable in plasma at 24-192 h in all subjects. There was little ($\leq 1-2.6$ ng/mL) or no PZ-128 detected in urine at any time point in all subjects consistent with the notion that the pepducin is not eliminated by the kidneys. The drug concentrations were highly linearly correlated with increasing dose at 0.25-8 h time points with R values of 0.980-0.998. Likewise, AUC and C_{max} of PZ-128 in plasma were linearly correlated with dose.

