6.5.5 Post-PZ-128/Placebo Infusion

1. Obtain vital signs including heart rate and blood pressure immediately after the completion of the study drug administration (i.e., Time=2 h).
2. Assess and record adverse events, including bleeding and efficacy endpoint events (MACE, stent thrombosis).
3. Collect blood samples for optional research according to site participation and subject's individual consent (see **Section 6.6.3.2**):
 - a. Samples for pharmacokinetics (plasma) and pharmacodynamics- platelet aggregation (whole blood) (PK/PD sub-study; participating sites only) will be drawn at the following time points: 30 min ± 5 min, 1 h ± 5 min, 2 h + 15 min (immediately after completion of infusion), and 6 h – 2 h (4 to 6 h) after the start of the PZ-128 infusion; and
 - b. Plasma sample for exploratory biochemical, inflammatory and metabolic markers will be drawn at the following time points: 2 h + 15 min (immediately after completion of infusion) and 6 h – 2 h (4 to 6 h) after the start of the PZ-128 infusion.

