One blood sample for DNA, RNA and microRNA analysis will be collected just before the administration of the study drug. Pharmacogenomics analysis will be undertaken to investigate whether DNA polymorphisms, RNA levels and microRNAs correlate with the expression of genes involved in thrombosis, inflammation, and cardiometabolic diseases and whether these genetic components correlate with PZ-128 outcomes. The samples will be analyzed by the sponsor and/or at one of the participating clinical sites under non-GLP conditions.

Subjects at Select Clinical Site(s) Participating in the PK/PD Sub-study

- **Pharmacodynamics- Platelet Aggregation (Whole Blood): Just Prior to Study Drug Infusion, Select Times During Hospitalization, 24-hour/Discharge, 14-day Visit**

Blood samples will be collected just before the administration of the study drug, then 30 minutes \pm 5 min, 1 hour \pm 5 min, 2 hours + 15 min (immediately after completion of infusion), 6 hours – 2 h (4 to 6 h) and 24 hours \pm 2 h or discharge (whichever occurs sooner) after the start of the study drug infusion and at the 14-day visit. After the 24-hour collection, if a subject remains in the hospital for \geq 48 hours, a blood sample will be collected just prior to discharge. The samples will be analyzed using light transmission aggregometry (LTA) on-site under non-GLP conditions.

- **Pharmacokinetics (Plasma): Just Prior to Study Drug Infusion, Select Times During Hospitalization, 24-hour/Discharge, 14-day Visit**

Blood samples will be collected just before the administration of the study drug, then 30 minutes \pm 5 min, 1 hour \pm 5 min, 2 hours + 15 min (immediately after completion of infusion), 6 hours – 2 h (4 to 6 h) and 24 hours \pm 2 h or discharge (whichever occurs sooner) after the start of the study drug infusion and at the 14-day visit. After the 24-hour collection, if a subject remains in the hospital for \geq 48 hours, a blood sample will be collected just prior to discharge. The samples will be analyzed by the sponsor/sponsor's designee under non-GLP conditions.

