6.7.1.4 Other Secondary Endpoints Related to Efficacy

Other secondary efficacy endpoints will include the following:

1. incidence of the individual components of the MACE composite through 30 days and 90 days after treatment;
2. incidence of definite or probable stent thrombosis through 30 days and 90 days after treatment;
3. inhibition of platelet aggregation induced by SFLLRN, thrombin, ADP, collagen and AYPGKF relative to baseline at several time points following treatment at select sites;
4. population pharmacokinetics at baseline and at several time points following treatment; and
5. effect of the investigator choice of P2Y12 inhibitor (i.e., clopidogrel versus prasugrel/ticagrelor) on the individual components of the MACE composite.

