7.9.2 Pharmacodynamics

At select sites, blood samples from each consenting participant will be analyzed onsite using Light Transmission Aggregometry (LTA) under non-GLP conditions at baseline and select time points following the start of the study drug administration as specified in **Section 6.6.3**.

The following will be measured:

- Inhibition of platelet aggregation (maximum and final) induced by SFLLRN 5-20 μM (or SFLLRN of equivalent potency) using blood collected in 0.4% sodium citrate.
- Inhibition of platelet aggregation (maximum and final) induced by AYPGKF 160 μM using blood collected in 0.4% sodium citrate.
- Inhibition of platelet aggregation (maximum and final) induced by collagen 4-20 $\mu\text{g/mL}$ using blood collected in 0.4% sodium citrate.
- Inhibition of platelet aggregation (maximum and final) induced by 5-20 μM ADP using blood collected in 0.4% sodium citrate.
- Inhibition of platelet aggregation (maximum and final) induced by thrombin 1 nM-1 μM using blood collected in 0.4% sodium citrate (with GPRP added for 1mM final concentration).

Maximal and final extent inhibition of platelet aggregation (IPA) from pre-dose baseline at Screening will be calculated at all subsequent time points using

$$\text{Percentage of Inhibition} = 100\% \times \frac{(\text{PAs} - \text{PA})}{(\text{PAs})}$$

Where PA is the mean response at the given time point, and PAs is the mean response at pre-dose baseline (Screening). Percentage inhibition will be restricted to the closed interval [0,100]; any data falling outside this range will be truncated to the appropriate limit. Individual peak inhibition of platelet aggregation (IPA_{max}) will be estimated as the highest IPA within the collection time period and TIPA_{max} will be the time to IPA_{max} for final extent and maximum extent of IPA.

The percentage inhibition of the specific agonist-induced platelet aggregation (final and maximum extent) will be summarized at the scheduled protocol time points using standard summary statistics for each treatment group. Mean plots showing changes within treatment groups across time will be presented. The derived PK and PD parameters will be summarized using standard summary statistics and graphical presentations.

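### Population PK is a secondary endpoint, but Section 7.9.1 plans only descriptive summaries by dose; half-life and distribution would rest on two declining-phase samples in subjects kept to about 24 h

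*Combined protocol and SAP*

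**What the plan says.** - **Endpoint.** Population PK is a secondary objective (Section 5.4). Section 6.7.1.4 lists the endpoint as "population pharmacokinetics at baseline and at several time points following treatment".
- **Analysis.** Section 7.9.1 states that "PK parameters will be calculated over time", names Cmax, AUC, half-life, clearance and distribution, and has them summarised by dose level. It adds: "Data will be presented using graphical summaries and descriptive statistics". Section 7.9.2 repeats the approach: "The derived PK and PD parameters will be summarized using standard summary statistics and graphical presentations". No population or mixed-effects model, covariate, or rule for concentrations below the assay limit appears in the document.
- **AUC.** Section 3.0 defines it as "Area under plasma concentration-time curve from zero to infinity", so it needs a terminal slope.
- **Sampling (Section 6.6.3.2).** PK blood is drawn before dosing; at 30 min, 1 h and just after the 2 h infusion ends; once at 4 to 6 h; at 24 ± 2 h, or at discharge if that is earlier; at discharge again if the stay reaches 48 h; and at day 14.
- **Kinetics.** The half-life is 1.3 to 1.8 h (Sections 4.1.2.2 and 6.7.2.2.9). For phase 1, Section 4.1.2.2 reports: "Drug was undetectable in plasma at 24-192 h in all subjects".

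**The concern.** The named endpoint and the described analysis do not match. Population PK normally means a model fitted to all subjects together, giving typical values, between-subject variability and covariate effects. Section 7.9.1 gives parameters and descriptive statistics, and the natural reading is one set of derived parameters per subject.

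The schedule makes this more than a question of labels. With a half-life under 2 h and nothing measurable at 24 h, few samples inform the decline. Two points fix a line exactly. They leave no residual degree of freedom, cannot show whether the decline is log-linear, and cannot separate a distribution phase from elimination, although distribution is a planned output.

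At stake is the quality of the PK description that Section 4.2.1 wants in hand before Phase 3.

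**Working it through.** **1. The plan's own figure.** Table 1 gives 7-8 PK draws and 35-40 mL. From the schedule: 1 pre-dose + 4 (0.5, 1, 2 and 4-6 h) + 1 or 2 (24 h or discharge, plus discharge after a long stay) + 1 (day 14) = 7 or 8 draws. At 5 mL each this is 35-40 mL. It reproduces.

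**2. Which draws are measurable.** Assume one-compartment kinetics and a 2 h infusion, with t½ = 1.3 or 1.8 h. The fraction of Cmax left at time T after the start is 2^(−(T−2)/t½).

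- 24 h: 22/1.3 = 16.9 or 22/1.8 = 12.2 half-lives have passed, leaving 0.0008% or 0.02%. This agrees with phase 1, so the 24 h and later draws carry no usable level.
- 4 h: 34% or 46%. 6 h: 12% or 21%. Both should be measurable.
- 8 h: 4% or 10%. 12 h: 0.5% or 2%. A same-day discharge sample may be measurable; phase 1 reports concentrations up to 8 h, but the assay limit is not given.

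A subject kept to about 24 h therefore has two declining-phase points. A subject discharged the same day may have three.

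**3. Share of AUC(0-inf) that is extrapolated.** With k = ln 2/t½, the share is (1 − e^(−2k)) · e^(−k(T−2)) / (2k).

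| t½ | k per h | 4 h draw | 6 h draw |
|---|---|---|---|
| 1.3 h | 0.533 | 0.656 × 0.344 / 1.066 = 21% | 0.656 × 0.119 / 1.066 = 7% |
| 1.8 h | 0.385 | 0.537 × 0.463 / 0.770 = 32% | 0.537 × 0.214 / 0.770 = 15% |

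**4. Precision of a two-point half-life.** Assume independent log-normal error with SD 0.15 (about 15% CV) in each sample. The log-ratio of the two concentrations has mean k(T−2) and SD √2 × 0.15 = 0.212, so its 5th-95th percentile range is k(T−2) ± 1.645 × 0.212 = k(T−2) ± 0.349. The half-life is ln 2 × (T−2) divided by that log-ratio.

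For t½ = 1.8 h and a 4 h draw, the log-ratio is 0.770 ± 0.349, or 0.421 to 1.119. The half-life is then 1.386/1.119 = 1.24 h to 1.386/0.421 = 3.29 h.

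| True t½ | 4 h draw | 6 h draw |
|---|---|---|
| 1.3 h | 0.98-1.93 h | 1.12-1.55 h |
| 1.8 h | 1.24-3.29 h | 1.47-2.33 h |

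For the 1.8 h, 4 h case, a 10% CV (± 0.233) gives 1.38-2.58 h and a 20% CV (± 0.465) gives about 1.1-4.5 h.

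**5. AUC and clearance.** A simulation of 200,000 subjects at 15% CV used linear-up/log-down AUC with extrapolation from the two-point slope. It gave AUC(0-inf) at about 0.86 to 1.17 of truth (5th-95th percentile) with a 6 h draw, and 0.83 to 1.40 in the worst case (4 h draw, t½ 1.8 h). Clearance is dose over AUC, so it inherits this. Both hold up better than half-life.

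**The case against.** The strongest reply is that the sampling is adequate for much of what is planned, and that detail was deferred. Most of this stands.

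- Cmax occurs at the end of infusion and is sampled there.
- AUC and clearance are roughly estimable, as step 5 shows.
- Section 6.1 foresees same-day discharge, so some subjects can supply a later measurable level.
- Section 7.2 promises a separate SAP and allows other software for PK. No separate SAP is in the supplied document, so silence here does not prove that no model was intended. It does leave the endpoint without a described analysis.

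Three stronger readings are tempting, and the documents do not support them.

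- *A reader might infer that half-life could double,* because a 4 h draw entered as 6 h gives 2.6 h for 1.3 h, or 3.6 h for 1.8 h. That requires nominal times. Section 7.9.1 does not call for them, and Section 8.2 has the PK samples labelled with collection date and time.
- *A reader might infer an AUC error of about 60%,* by drawing a straight line from a 5 h sample to zero at 24 h. The plan states no such rule, and its definition of AUC to infinity points to extrapolation from a slope. With a linear trapezoid to the last measurable sample plus that extrapolation, AUC is only 1-18% high.
- *A reader might infer that the exposure-response aim cannot be met.* The aim in Section 4.2.1 is the relation between PK and inhibition of platelet aggregation. PK and aggregation samples share the same time points, so matched pairs are available without half-life or AUC.

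**Conclusion.** The concern holds in a limited form. A stated secondary endpoint has no matching analysis, and the described alternative is weakest for half-life and distribution in subjects kept to about 24 h. AUC(0-inf) and clearance are affected less, and observed Cmax is not affected by the sparse decline. It would be wrong to say that the schedule cannot support these parameters at all.

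The sizes in steps 3 to 5 rest on one-compartment kinetics. Those in steps 4 and 5 also rest on an assumed assay CV; neither assumption comes from the documents. The count of two declining-phase points rests on phase 1 detectability and would change if the assay were more sensitive. This is an optional sub-study at selected sites, reported descriptively, and the primary safety conclusion is untouched. The change is a worthwhile improvement rather than a necessary correction.

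**What to change.** In Section 7.9.1, name a nonlinear mixed-effects model on all PZ-128 concentrations as the analysis of the population PK endpoint. Specify:

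- actual sampling times and actual infusion start, stop and interruption times (Section 6.4.7.7 allows interruption of up to 1 hour);
- likelihood-based handling of concentrations below the assay limit;
- body weight as a covariate (Section 6.3.2 admits 60 to 175 kg);
- clearance, volume, half-life and AUC reported from the model.

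Keep observed Cmax and any non-compartmental summaries by dose as descriptive support. The spread of draws over 4 to 6 h and over discharge times then becomes useful, because the model pools it across subjects and also uses the samples taken during infusion.

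The cost is more analysis work: model building and checking, written down before unmasking. No extra samples, visits or blood volume are needed.
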